[name], BAMC/PI will conduct placental gross and microscopic evaluations. Frozen tissue biopsies for CAMD will be used for characterization and identification of specific immunological, inflammatory, and hormone biomarkers changes. Tissue specimens will be homogenized and divided into two groups for analysis: (1) RT-PCR for RNA expression; (2) Multiplexed panel for protein expression. Response groups will be divided into: (1) Th1, (2) Th2, (3) Hormonal, and (4) Oxidative Stress, and some of their specific factors.

The coded, flash frozen placental tissue will be stored in a -80°C freezer until they are packed by the PI and/or pathology resident into storage boxes appropriate for transport to the Center for Advance Molecular Detection (CAMD). Dry ice will not be required for immediate transport between BAMC pathology lab and CAMD. Project coordinator and/or the research personnel will sign for the specimens and verify packaging. They will be responsible to ensure the specimens are taken directly to the CAMD lab, where they will be signed in accordance to CAMD SOP 4-4. Specimens will be stored at -80°C, until sufficient specimens are available for a trimester batch run. [name], the senior scientist at the 59 MDW S&T, and a co-investigator on the study will be responsible for all tissue specimens and the requisite data.

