Patients' will be consented for the use of their placental tissue. Once the analysis has been run and the data is analyzed with the psychosocial and microscopic data, one of three things will occur according to the participant consent: 1) the tissue will be destroyed, 2) the tissue will be maintained as a coded specimen within a tissue repository at CAMD, and/or 3) coded slides will be maintained for medical student use at UIW School of Medicine. The tissue will be maintained until the completion of all data analyses as re-analysis might occur. In the process of data cleaning and analysis, questions may arise regarding the results requiring re-running of that "batch." At which time it is determined that there is no further need for the tissue, all coded specimens and data kept at 59MDW, BAMC, and UIW will be handled and disposed of in accordance with federal regulations and will be destroyed at the end of all data mergers, or no later than at the closure of the study, based on AFI 33-332, "The Air Force Privacy and Civil Liberties Program" and the National Institute Standards and Technology Special Publication (NIST SP 800-88) for the approved methods to destroy PII. Note, the only items maintained at UIW, are the coded histology slides (until completion of the study, at which time, the slides will no longer be coded but maintained within a slide "library" for student review purposes. There will be no patient information associated with the slides or tissue specimens. Results of the questionnaires (maintained in an SPSS de-identified dataset), and de-identified outcomes data IF the CRADA is obtained will be utilized by study PIs for completion of reports and publications. UIW will not be maintaining or storing any tissue samples or copies of patient medical records.

10.3 At any point in the study, will you request, use, or access health information in any form, including verbal, hard copy and electronic?

Yes No

10.4 Review the definitions below and respond to the following two questions. If you are not sure of the answers, email [contact] for assistance.

The Military Health System (MHS) is defined as all DoD health plans and DoD health care providers that are organized under the management authority of, or in the case of covered individual providers, assigned to or employed by, the Defense Health Agency (DHA), the Army, the Navy, or the Air Force

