Statistical Analysis System (SAS) version 9.4 will be used for all analyses. Descriptive statistics (mean, sd, median for each continuous variable and proportions for each discrete variable) will be used to describe the sample. Linear or generalized linear mixed models will be developed for all variables, prenatal anxiety, self-esteem, family adaptability/cohesion, prenatal depression and perceived support, as well as the protein and RNA values, in order to examine their association with placental metrics across pregnancy. The linear (mixed) model will be used for all normally distributed continuous data. In the case of skewed continuous outcome data, the generalized linear (mixed) model with gamma distribution and log-link will be chosen. For binary or dichotomized outcomes, a mixed model logistic regression will be chosen. Measurement times (dates of data collection by gestational age), will be included in the models as predictors when available with and without adjusting for the participant's age, employment status, prior deliveries, marital/partner status, education, deployment of partner during pregnancy, military branch of service of participant or partner, ethnicity, military rank of participant or partner and MOPS group. In the case of dual military couples, the rank and service of the active duty woman will be used. The final models will be determined with backward elimination procedure. Timing of data collection (weeks gestation), may also be chosen as a random effect within the model. Additionally, each prenatal variable (prenatal anxiety, self-esteem, depression, family adaptability/cohesion and resilience) will be longitudinally regressed on measurement time to obtain the slope through best linear unbiased predictor (BLUP). The resulted individual slopes will be used to determine any significant effects for prenatal psychosocial scores to pregnancy complications, birth and infant outcomes, and to the physiologic data (both placental scores and biomarker data).

To examine if anxiety mediates the relationship between biomarkers and birth outcomes, we will develop a Baron and Kenny (1986) mediation model assess the relationships as in Bauer and Preacher (2006). We will conduct three mixed regression models adjusted for all appropriate covariates:

1. Regress birth outcome on biomarker.
2. Regress birth outcome on biomarker and anxiety.
3. Regress anxiety on biomarker.

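### Placental biomarkers are assayed in periodic runs, but the named covariates for the protein and RNA models include no run or date term; this costs precision and can confound associations with variables that also differ by run.

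*Protocol*

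**What the plan says.** Under Protocol section 10.2, flash-frozen tissue is held at -80°C "until sufficient specimens are available for a trimester batch run". Each specimen is homogenised and split between RT-PCR for RNA and a multiplex panel for protein. The same section keeps tissue until all analyses are finished, so that a batch can be run again if data cleaning or analysis raises questions about its results.

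Section 11.6 plans linear or generalized linear mixed models for the psychosocial measures "as well as the protein and RNA values, in order to examine their association with placental metrics across pregnancy". The models are fitted "with and without adjusting for the participant's age, employment status, prior deliveries, marital/partner status, education, deployment of partner during pregnancy", and the list then continues with "military branch of service of participant or partner, ethnicity, military rank of participant or partner and MOPS group". On time, the plan says "Measurement times (dates of data collection by gestational age), will be included in the models as predictors". The only random effect it names is weeks of gestation. Final models are reached by backward elimination. Individual slopes of the psychosocial scores are also to be related to the biomarker data.

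The three mediation regressions, all of which use a biomarker, do not list their covariates; they are only to be adjusted for whichever are appropriate. Section 11.1 adds correlations between the biomarker groups.

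**The concern.** Placentas become available only at delivery, so filling runs as specimens accumulate ties run to delivery date. The protocol thereby creates a technical grouping of the biomarker values, and the stated covariates do not capture it. Gestational age at questionnaire completion says nothing about which run a placenta was assayed in.

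Two consequences need to be kept apart. First, any between-run variance stays in the residual of a biomarker outcome, or acts as measurement error in a biomarker predictor. That lowers precision. Second, if the variable on the other side of the association also differs between runs, run becomes a confounder and the test no longer holds its nominal level.

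The second condition is plausible here for two reasons. Section 10.1 plans recruitment from November 2019 to March 2021, and Table 2 includes a pandemic-related stress scale, so psychosocial scores may differ between early and late deliveries. The planned biomarker-biomarker correlations can pair two variables measured in the same runs, with no need for any drift in anxiety.

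**Working it through.** **The plan's own figure.** Section 11.5 asks for 1200 deliveries at 80% power and significance 0.05, with 45% pathology, but states no effect size. The 1200 can therefore be neither confirmed nor refuted, only back-solved (two-sided test assumed):

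- Correlation: tanh[(1.960 + 0.842)/√(1200 − 3)] = tanh(0.0810) = 0.081.
- Mean difference, 540 against 660: 2.802 × √(1/540 + 1/660) = 0.163 SD.

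The value r = 0.081 is used below as the effect that 1200 can detect.

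**Assumed inputs.** Reading a trimester run as quarterly, 17 months of recruitment give 17/3 ≈ 6 runs, and 1200/6 = 200 specimens per run. Batch ICC means the share of a variable's variance that lies between runs. The protocol gives no value, so the ranges are 0.05-0.30 for the biomarker and 0-0.05 for the exposure.

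**Method.** Simulation with 5000 repetitions per cell (Monte Carlo SE √(0.05 × 0.95/5000) = 0.3 points near 5%), comparing a model without batch against one with batch as a fixed effect. Approximate check on type I error without batch: 2 × [1 − Φ(1.96/√(1 + 199 × ICCx × ICCy))].

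**Type I error without batch (nominal 5%)**

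| Exposure ICC | Biomarker ICC 0.05 | 0.10 | 0.20 | 0.30 |
|---|---|---|---|---|
| 0 | 4.5% | 4.8% | 4.6% | 5.5% |
| 0.01 | 6.4% | 7.6% | 9.5% | 11.0% |
| 0.02 | 7.1% | 9.3% | 13.4% | 16.1% |
| 0.05 | 10.2% | 13.1% | 22.9% | 28.9% |

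Example of the check at 0.02 and 0.10: 1 + 199 × 0.002 = 1.398; 1.96/√1.398 = 1.658; tail probability 9.7%, against 9.3% simulated. At 0.05 and 0.20 the approximation gives 25.7% against 22.9%, so it runs somewhat high there.

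**Two biomarkers in the same runs**, truly unrelated, with independent run shifts: 9.4%, 21.1% and 46.8% when both ICCs are 0.05, 0.10 and 0.20.

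**Sensitivity to the number of runs** (ICCs 0.02 and 0.10): 10.7% with 4 runs, 7.7% with 8.

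**Power at r = 0.081, exposure unrelated to run.** Analytic form without batch: Φ[atanh(0.081 × √(1 − ICC)) × √1197 − 1.96].

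| Biomarker ICC | Without batch, simulated | Without batch, analytic | With batch, simulated |
|---|---|---|---|
| 0 | 80% | 80% | 80% |
| 0.05 | 79% | 78% | 80% |
| 0.10 | 77% | 76% | 81% |
| 0.20 | 71% | 71% | 79% |
| 0.30 | 69% | 65% | 81% |

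With batch as a fixed effect, type I error is 4.5-5.5% in every scenario.

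**The case against.** The strongest reply is that run adjustment, calibrators and normalisation usually sit in a laboratory procedure or a separate SAP, neither of which is at hand, and that section 11.6 does not forbid a batch term. This has force as regards calibration, and no fault is found with its absence from the protocol. Calibration reduces between-run variance but need not remove it. Section 11.6 also goes further than staying silent: it names the covariates, the time term and the elimination procedure, and a team that follows it as written will fit the biomarker models without run.

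It can also be said that the first two aims are exploratory and that the loss is slight at modest run variation: 1 to 3 power points at a biomarker ICC up to 0.10. Both are true, and they limit the weight of the point.

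A reader might infer that batch is shut out of every model. The text does not support that, since the mediation regressions leave their covariates open. Nor is the re-run provision an admission that assays are expected to fail; it is a quality-control safeguard, and it suggests that results can be traced to a batch.

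**Conclusion.** The point holds in conditional form. Assays are run in batches, and the named covariates, time term and random effect for the protein and RNA models do not capture run. If between-run variation is material, precision is lost: power at r = 0.081 falls to between 79% and 71% for biomarker ICCs of 0.05 to 0.20.

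A reader might go further and infer that leaving batch out inflates false positives in every biomarker analysis. The check does not support this. Where the exposure does not differ by run, type I error stays near 5% even at a biomarker ICC of 0.30. Inflation to about 6-23% needs an exposure ICC of 0.01-0.05 together with a biomarker ICC of 0.05-0.20, and the upper end needs the top of both ranges at once. For pairs of biomarkers sharing runs the range is about 9-47%. The recruitment window and the pandemic scale make drift in the scores plausible, but the protocol does not establish it.

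Every ICC, the number of runs and their equal size are assumptions. The figures show what could happen and do not predict this study's error rate. The change is worth making because it is cheap and because a run identifier not captured at the assay may be hard to recover later.

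**What to change.** - Record the run and plate identifier for each RT-PCR and each multiplex result, separately for the two assays. After a re-run, keep the identifier of the run that produced the analysed value.
- In section 11.6, state that batch enters every model that uses a biomarker: the protein and RNA models, the analyses of individual slopes against biomarkers, the correlations between biomarker groups, and the three mediation regressions.
- Exempt batch from backward elimination, and keep it in the versions fitted without the demographic covariates.
- Say whether batch is a fixed or a random effect. The figures above are for a fixed effect. A random intercept accounts for run variance but does not by itself fully remove confounding between run and exposure.

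Cost: one recorded field per assay result, one or two sentences in section 11.6, and about 5-6 degrees of freedom out of 1200 (5 for 6 runs). The real downside is that genuine calendar-time variation in the psychosocial scores is partly absorbed by the batch term, so the associations then rest mainly on differences between women assayed in the same run.

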11.0 Statistical/Data Analysis Plan

11.1 Statistical Considerations:

List the statistical methods to be used to address the primary and secondary objectives, specific aims, and/or research hypotheses. Explain how missing data and outliers will be handled in the analysis. The analysis plan should be consistent with the study objectives. Include any sub-group analyses (e.g., gender or age group). Specify statistical methods and variables for each analysis. Describe how confounding variables will be controlled in the data analysis

For characterization and identification of specific immunological, inflammatory, and hormone biomarkers changes, placental tissue biopsies taken from the same locations as the tissue for the paraffin blocks, will be flash-frozen in liquid nitrogen prior to being sent (by courier) to the 59th MDW Center of Advanced Molecular Detection (CAMD) at JBSA-Lackland. Once received, each biopsy will be homogenized and divided into two groups for analysis: (1) RT-PCR for RNA expression; (2) Multiplexed panel for protein expression. Response groups will be divided into: (1) Th1, (2) Th2, (3) Hormonal, and (4) Oxidative Stress, and some of their specific factors are summarized in **Table 1**.

Table 1: Select Immunological, Hormonal, and Oxidative Stress Factor for Analysis.

Th1	Th2	Th17 (Treg)	Oxidative Stress	Stress Hormone
IFN-γ	IL-3	IL-17	Hydrogen Peroxide	Prostaglandin E2
TNF-β	IL-4	IL-23	Nitric Oxide Synthase Family	Cortisol
TNF-α	IL-5	TGF-β	S-glutathionylation	CRH (HPA Axis)
IL-12p70	IL-10		C-reactive Protein	ATCH
IL-18	IL-13			DHEA
IL-1β	LIF			
IL-6				
IL-2				
MIP-1α				

Specifically, analysis will explore the physiological correlations between the biomarker groups as a response to psychosocial factors and in relation to histopathological analysis. The psychosocial measures obtained at various timepoints in first, second, and third trimester are presented in Table 2.

Table 2.

Variable	Measurement	Collection Timepoints
Prenatal Maternal Stress and Anxiety – (Prenatal Adaptation)	Lederman Prenatal Self-Evaluation Questionnaire (PSEQ-sf) , 53 items (7 scales). Higher scores on a scale indicate greater anxiety related to the formulation of the motherhood role. Biochemical markers of stress in labor, and labor and postpartum outcomes were used to provide convergent and divergent construct validity; Cronbach's alpha coefficients for the scales range from $\alpha = .75$ to $.92$. [name] obtained similar coefficients in her military populations. The instrument has been factored with a military population and all 7 scales remained distinct. The scales measure the level of anxiety the woman is experiencing relative to the particular dimension.	Pregnancy: Initial, 12, 16, 24, & 32 weeks
Self-Esteem	Rosenberg Self-Esteem Scale (RSE) , 10-item scale measuring the degree to which one values oneself. The possible range of scores is 10 to 40, with higher scores indicating higher self-acceptance. The Cronbach's alpha reliabilities range from $.84$ to $.90$. The construct validity of the instrument was demonstrated by examining its conformity to theoretical predictions. The test-retest reliability was found to be $r = 0.85$. This instrument was used in the pilot M.O.M.S. project with good results.	Pregnancy: Initial, 12, 16, 24, & 32 weeks
Family Adaptability and Cohesion	Family Adaptability and Cohesion Evaluation Scales (FACES II) 30-item (2 scales) measuring the ability of the family (couple) to change its roles, rules, and power structure. High scores on both scales indicate extreme (dysfunctional) responses and low scores indicate flexibility, adaptability, or balance. Cronbach's alpha coefficients for FACES II couples version are 0.87 for cohesion and 0.78 for adaptability from a National Survey of 1000 families. [name] has used this instrument with good results.	Pregnancy: Initial, 12, 16, 24, & 32 weeks
Prenatal Depression	Edinburgh Postnatal Depression Scale (EPDS) is a 10-item self-report scale validated for use during pregnancy and the postpartum period. Scores range from 0-30; higher scores are associated with higher depression. Scores of 12 or greater will be associated with prenatal depression. The Cronbach's alpha has been established as 0.80.	Pregnancy: Initial, 12, 16, 24, & 32 weeks
Perceived Support	Social Support Index (SSI) is a 17-item instrument designed to measure the degree to which families are integrated into the community, view the community as a source of support, and feel that the community can provide emotional, esteem, and network support. The instrument uses a 5-point Likert scale with higher scores indicating more perceived, anticipated social support. The SSI had a .40 validity coefficient with the criterion measure of family well-being. Construct validity was assessed in a study with over 1,000 families and the	Pregnancy: Initial, 12, 16, 24, & 32 weeks

	perceived support was positively correlated with a family's sense of fit within the community ($r = .40$). The internal reliability of the SSI was reported as $\alpha = .82$ and test-retest reliability as $\alpha = .83$.	
Military Family Commitment and Stress	Family Index Coherence (FIC) is a 17-item instrument developed to measure the degree to which families feel committed to the military mission and identify a subscale of family coping to manage life changes and stresses. The instrument uses a 4-point Likert scale ranging from "Strongly Agree" (3) to "Strongly Disagree" (0). The internal reliability of FIC has been established as $\alpha = .82$ and test-retest reliability of $\alpha = .86$.	Pregnancy: Initial, 12, 16, 24, & 32 weeks
Resilience	Brief Resilience Scale (BRS) is a 6-item instrument developed to measure the concept of "bouncing back from stress." The instrument uses a 5-point Likert scale ranging from "Strongly Agree" (5) to "Strongly Disagree" (1) with a neutral measure (3). The internal reliability for the BRS has been established as .80-.91. ²⁷ The test-retest for one month ranged from .63-.69 in two samples.	Pregnancy: Initial, 12, 16, 24, & 32 weeks
Pandemic Related Stress /Anxiety	The Pandemic Related Pregnancy Stress Scale (PREPS) , 17 item instrument developed to measure the thoughts and concerns pregnant women might have due to the COVID-19 pandemic using 3 constituent factors: preparedness stress, perinatal infection stress, and positive appraisal. The response scale ranges from 1= Very Little to 5= Very Much. Stress scales are internally consistent with Cronbach's alpha coefficient is >0.80.	Pregnancy: Initial, 12, 16, 24, & 32 weeks

Pregnancy and neonatal outcome data including gestational age at delivery, infant birthweight, mode of delivery, and pregnancy complications, including pre-eclampsia, gestational hypertension, gestational diabetes, and perinatal and neonatal infections, will be collected from the maternal and infant medical records. If missing from the demographic data form, maternal parity, gestational age at first prenatal appointment, ethnicity, beneficiary status (active duty vs. dependent), smoking history, and other medical history will be obtained from the obstetrical record. The participants have signed a HIPPA form as part of the MOMS study and all data mentioned is being collected as a part of this study.

11.2 Sample Size:

1200

11.3 Total number of subjects requested (including records and specimens):

1200

11.4 If you are recruiting by study arm, please identify the arms of the study and how many subjects will be enrolled in each arm

N/A

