Resilience	Brief Resilience Scale (BRS) is a 6-item instrument developed to measure the concept of "bouncing back from stress." The instrument uses a 5-point Likert scale ranging from "Strongly Agree" (5) to "Strongly Disagree" (1) with a neutral measure (3). The internal reliability for the BRS has been established as .80-.91. ²⁷ The test-retest for one month ranged from .63-.69 in two samples.	Pregnancy: Initial, 12, 16, 24, & 32 weeks
Pandemic Related Stress /Anxiety	The Pandemic Related Pregnancy Stress Scale (PREPS), 17 item instrument developed to measure the thoughts and concerns pregnant women might have due to the COVID-19 pandemic using 3 constituent factors: preparedness stress, perinatal infection stress, and positive appraisal. The response scale ranges from 1= Very Little to 5= Very Much. Stress scales are internally consistent with Cronbach's alpha coefficient is >0.80.	Pregnancy: Initial, 12, 16, 24, & 32 weeks

Placental tissue collected after birth will be used to obtain histologic, microscopic, and molecular data. Pregnancy and neonatal outcome data including gestational age at delivery, infant birthweight, mode of delivery, and pregnancy complications, including pre-eclampsia, gestational hypertension, gestational diabetes, and perinatal and neonatal infections will be collected from the maternal and infant medical records. If missing from the demographic data form, maternal parity, gestational age at first prenatal appointment, ethnicity, beneficiary status (active duty vs. dependent), smoking history, and other medical history will be obtained from the obstetrical record. Participants will sign a HIPAA form providing permission to access their obstetrical records (prenatal and inpatient) for the pregnancy complications and neonatal/birth outcomes data.

Source of Research Material	Standard Care? (Y/N)
Placental tissue	Y
Prenatal questionnaire booklet	N
Outpatient Record Data (prenatal EDC verification/pregnancy complications)	Y
Inpatient Record Data (birth outcomes)	Y

Setting:

All women attending OB orientation have had their pregnancies verified through the OB clinic. Therefore, additional screening is not required to confirm they are pregnant. The study inclusion criteria includes, being a pregnant woman, in the first trimester, Active Duty or a DoD beneficiary. The women may also be participants in the Mentors Offering Maternal Support study at BAMC.

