11.5 Please provide a justification for your sample size

There are approximately 1500 deliveries a year at the San Antonio Military Medical Center. Approximately 1100 (73%) of delivered placentas are sent for pathologic examination. Approximately 45% of the placentas are found to have some type of pathology. Given the percentage of placental pathology within this population, 1200 deliveries would be required to compare differences in placental tissue to psychosocial measures with a power of 80% and significance of .05.

11.6 Data Analysis Plan: Complete description: Background, Objectives, Design, Step by Step how the project is going to be done, Data analysis plan:

Data Analysis Plan:

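### Maternal weight, height or BMI is named neither for abstraction nor in the 11.6 adjustment list, so associations with complications, birthweight and inflammatory markers may be confounded by body size

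*Protocol*

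**What the plan says.** Section 11.1 (Statistical Considerations) lists the maternal items that the obstetrical record is to supply where the demographic form has gaps: "maternal parity, gestational age at first prenatal appointment, ethnicity, beneficiary status (active duty vs. dependent), smoking history, and other medical history". Section 10.1 gives the same list and ends it in the same way: "smoking history, and other medical history will be obtained from the obstetrical record". The demographic form itself is not reproduced.

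Section 11.6 (Data Analysis Plan) runs its models with and without adjustment. The adjusters are the participant's age, then "employment status, prior deliveries, marital/partner status, education, deployment of partner during pregnancy, military branch of service of participant or partner, ethnicity", then military rank and MOPS group. Final models come from backward elimination. Each woman's slope on the psychosocial measures is then related to complications, birth and infant outcomes, placental scores and biomarkers; no covariates are restated for that step. The three mediation regressions are to be adjusted for whatever covariates are appropriate, without naming them.

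The outcome data in 10.1 and 11.1 include birthweight, pre-eclampsia, gestational hypertension and gestational diabetes. Table 1 in 11.1 includes C-reactive protein, IL-6 and TNF-α. The only weight mentioned anywhere in the supplied text is the infant's.

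**The concern.** Anxiety, depression and the other scores are observed, not assigned, so any shared cause of score and outcome can produce an association. Early-pregnancy body size is an obvious candidate. That it affects the three complications, birthweight and inflammatory markers is general clinical knowledge, taken here as an assumption. The protocol's own background (9.2) says only that physical condition can significantly affect pregnancies.

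This is not a detail that can be left to a later analysis plan. The form's prompt in 11.1 asks how confounding will be controlled, and 11.6 answers with a specific list. Backward elimination can only remove candidates; it cannot bring in a variable that was never offered. An analysis plan also cannot use a field that nobody recorded.

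At stake is whether a significant score-marker, score-complication or marker-birth outcome association could simply reflect body size.

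**Working it through.** **Inputs from the protocol.** Section 11.5 says "1200 deliveries would be required to compare differences in placental tissue to psychosocial measures with a power of 80% and significance of .05", and "Approximately 45% of the placentas are found to have some type of pathology". It states no effect size, SD or dropout, and no sidedness (two-sided assumed here).

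**The plan's own figure.** 1200 cannot be reproduced without an effect size, so I solved backwards.
- Pathology split: 0.45 × 1200 = 540 against 660. Detectable difference = (1.960 + 0.842) × √(1/540 + 1/660) = 0.163 SD at 80% power.
- Detectable correlation = tanh[(1.960 + 0.842)/√1197] = 0.081.

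These figures give a scale: a spurious correlation of a few hundredths is not negligible beside 0.081. The sample size is neither right nor wrong because of this point.

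**Inputs not in the protocol (assumptions).** BMI-score correlation 0 to 0.20; BMI-marker correlation 0.15 to 0.30; no true score-marker association; no other covariates in the model.

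**Formulas.** Spurious correlation r = r(score, BMI) × r(marker, BMI). With z = atanh(r) × √1197, the rejection rate is Φ(z − 1.96) + Φ(−z − 1.96).

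Example: r = 0.20 × 0.30 = 0.06; z = 0.0601 × 34.60 = 2.08; rejection = Φ(0.12) + Φ(−4.04) = 54.7%.

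Rejection rate at nominal .05, N = 1200 (spurious r in brackets):

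| BMI-score correlation | BMI-marker 0.15 | BMI-marker 0.20 | BMI-marker 0.30 |
|---|---|---|---|
| 0 | 5% (0) | 5% (0) | 5% (0) |
| 0.05 | 5.8% (0.0075) | 6.4% (0.010) | 8.1% (0.015) |
| 0.10 | 8.1% (0.015) | 10.6% (0.020) | 18.0% (0.030) |
| 0.20 | 18.0% (0.030) | 28.3% (0.040) | 54.7% (0.060) |

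**Binary complication, also on assumed values.** If p1 and p0 are the shares of women with obesity among high and low scorers, and RR is the risk ratio for obesity, the spurious risk ratio is [1 + p1(RR − 1)]/[1 + p0(RR − 1)].
- p1 = 0.40, p0 = 0.30, RR = 2: 1.40/1.30 = 1.08.
- Same shares, RR = 3: 1.80/1.60 = 1.13.
- Equal shares: 1.00, whatever the RR.

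**Marker and birth outcome.** The first mediation regression has birth outcome on biomarker. BMI confounds it if BMI affects both of these; no link between BMI and anxiety is needed.

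**With BMI in the model.** If its effect is linear and it is measured without error, the spurious part is about zero and rejection returns to about 5%.

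**The case against.** The other side has several good points.

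- **Collection.** A reader might infer that BMI is not collected at all. The documents do not show that. The demographic form is not reproduced, and the record list ends with an open medical-history item, so only absence by name is established. Being on the record list would not be enough in any case: smoking history is there and is still not among the 11.6 adjusters.
- **Openness of the adjustment.** The mediation models leave their covariates unspecified, so BMI could enter them. The fixed list cannot be read as governing every model.
- **Slopes, not levels.** Complications and biomarkers are tested against individual slopes over gestation. A BMI correlation with score level does not imply one with change. If the slope correlation is 0.05, rejection is about 6% to 8%; if it is zero, 5%.
- **Tissue.** The markers are measured in placental biopsies, and section 14.6 says no blood is taken. Nothing in the documents says how body size relates to markers in this tissue.
- **Direction.** A reader might infer bias towards hypotheses 1a and 2a. This is not shown. Hypothesis 1a concerns placental pathology, and no BMI-pathology link is given. Hypothesis 2a concerns Th1 relative to Th2 and Th17, which a general rise in cytokines need not shift.
- **Repair.** A reader might infer that the gap can never be closed. Section 10.14 keeps the participant key until final reports are complete, so records could still be reopened during analysis. The same section also wants identity links destroyed as soon as possible, so that opportunity is limited.
- **Causal path and listed covariates.** BMI may lie partly on a causal path, and age, ethnicity, education or rank may absorb some of its effect.

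These points limit the size and certainty of the claim. They do not remove the gap: the plan as written names no measure of maternal body size and gives it no place in the listed adjustment.

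**Conclusion.** The point holds as a risk of confounding, not as demonstrated bias. What is certain from the text is that maternal weight, height and BMI are not named for abstraction or in the 11.6 list, while outcomes and markers plausibly related to body size are analysed without randomisation. What is supported is that score-outcome, score-marker and marker-birth outcome associations may be confounded.

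The 5% to 55% rejection range rests on correlations that the documents do not give, on score level rather than slope, and on a model without the other covariates. Its lower end, with no BMI-score link, means no bias at all in the score-marker tests. The actual size for slopes and for placental-tissue markers is unknown. The stronger statement, that these associations are confounded by body size, is not supported. The change is still worth making because it is cheap and removes an obvious alternative explanation.

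**What to change.** In 10.1 and 11.1, name maternal height and weight at the first prenatal visit as items abstracted from the obstetrical record, giving early-pregnancy BMI. Do this while the participant key still exists.

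In 11.6, add BMI as a continuous covariate, exempt from backward elimination, to the adjusted models for placental metrics, to the slope models for complications, birth outcomes and biomarkers, and to all three mediation regressions. Keep the planned presentation with and without adjustment, so that a reader can see how far BMI moves each estimate if it is partly on the causal path.

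The cost is two fields from a record the study already has permission to open, one term per model, a little abstraction time and some missing values. The sample size of 1200 is unchanged.
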